7.2 Visit 2, Day 5-10 (Test of Cure Visit)

Subjects will have the following:

1. Interim medical history for assessment of specific symptoms that are potentially related to fluoroquinolone use as described in section 9, Assessment of Safety, and interim sexual history
2. Review of signs and symptoms at site of infection since the previous visit
3. Review of new antibiotics or concomitant medications contraindicated with ciprofloxacin
4. Targeted physical exam
5. One swab for *N. gonorrhoeae* culture and one swab for NAAT and *gyrA* serine 91 genotype from the throat*
6. One swab for *N. gonorrhoeae* culture and one swab for NAAT and *gyrA* serine 91 genotype from the rectum*
7. One swab for *N. gonorrhoeae* culture from the urethra (males)*
8. Urine specimen for NAAT and *gyrA* serine 91 genotype (males)*
9. Cervical swab for *N. gonorrhoeae* culture (females)*
10. Cervical or vaginal swab for NAAT and *gyrA* serine 91 genotype (females)*
 - ***Note 1:** Repeat samples to be collected only from those anatomical sites swabbed for *N. gonorrhoeae* culture or NAAT at Visit 1
 - ***Note 2:** *GyrA* assay is required only if NAAT is positive
11. Reminder to bring sex partners in for testing and treatment, if needed
12. Reminder that test results will be provided to subjects by phone call (Visit 3, Day 11-14)

Women diagnosed with bacterial vaginosis (BV) will receive treatment according to local standard of care.

7.3 Visit 3, Day 11 to 14 (Test of Cure Results)

1. Test results will be provided to subjects by phone call.
2. Subjects whose Visit 2 (Day 5-10) *N. gonorrhoeae* culture and NAAT results are negative will have completed participation in the study; no further follow-up is required.
3. Subjects who are *N. gonorrhoeae* culture positive or NAAT positive will be referred for standard of care treatment for *N. gonorrhoeae*.
4. Reminder to bring sex partners in for testing and treatment, if needed

7.4 Unscheduled/Early Termination Visit

For an unscheduled visit at the subject's request or the site investigator's recommendation, subjects will have the following:

1. Interim medical history for assessment of specific symptoms that are potentially related to fluoroquinolone use as described in section 9, Assessment of Safety, and interim sexual history
2. Review of signs and symptoms at site of infection since the previous visit
3. Review of new antibiotics or concomitant medications contraindicated with ciprofloxacin
4. Targeted physical exam
5. Reminder to abstain from sexual intercourse or use condoms during any sexual contact until the Test of Cure Visit (Visit 2, Day 5-10) is complete
6. Reminder to bring sex partners in for testing and treatment, if needed
7. Reminder to return for follow-up visit

For an early termination visit, subjects will have the following:

1. Interim medical history for assessment of specific symptoms that are potentially related to fluoroquinolone use as described in section 9, Assessment of Safety, and interim sexual history
2. Review of signs and symptoms at site of infection since the previous visit
3. Review of new antibiotics or concomitant medications contraindicated with ciprofloxacin
4. Targeted physical exam
5. Reminder to bring sex partners in for testing and treatment, if needed

8 STUDY PROCEDURES/EVALUATIONS

8.1 Clinical Evaluations

Discuss pertinent medical history for assessment of specific symptoms that are potentially related to fluoroquinolone use as described in section 9, Assessment of Safety, and sexual history (including assessment of signs and symptoms) will be obtained by interview of the subjects at Visit 1 prior to study treatment. Subjects will be asked if they can swallow pills.

- For female cervicovaginal infections, subjects will be classified as symptomatic if they report any of the following symptoms: abnormal vaginal discharge, abnormal vaginal bleeding, or pain during intercourse.
- For male urethral infections, subjects will be classified as symptomatic if they report any of the following symptoms: urethral discharge or pain with urination.
- For testing of rectal swab specimens, subjects will be classified as symptomatic if they report any of the following symptoms: anorectal pain, anorectal discharge, or anorectal bleeding.
- For testing of pharyngeal swab specimens, subjects will be classified as symptomatic if they report having a sore throat.
- For all specimen types, subjects will be considered asymptomatic if they do not endorse these symptoms.

At Visit 2 (Day 5-10) and unscheduled visits, an interim medical history will be obtained by interview if the subject notes any changes since the previous visit in specific symptoms that are potentially related to fluoroquinolone use as described in section 9, Assessment of Safety. The interim medical history should include an assessment for new medical conditions.

Sexual history including sexual orientation will be obtained by interview of the subjects at Visit 1. At Visit 2 (Day 5-10) and unscheduled visits, subjects will be queried regarding sexual activity and condom use since the previous clinic visit.

Medications history (concomitant medications contraindicated with ciprofloxacin) will include a review of all current medications and medications taken 30 days prior to study enrollment. Assessment of eligibility will also include a review of all permitted and prohibited medications per the Subject Inclusion and Exclusion Criteria (see section 5).

A targeted physical exam will be performed based on subject's clinical history. The exam will be performed by appropriate study personnel to assess general physical condition and will at a minimum include the following areas/systems: throat, genitals, and rectum. A speculum exam will be performed on females. All physical examinations will be performed by a study clinician licensed to make medical diagnoses. At visits following

Visit 1, a targeted physical examination may be conducted based on interim medical history.

8.2 Laboratory Evaluations

8.2.1 Clinical Laboratory Evaluations

Prior to the study implementation period, each laboratory will verify the performance of the *gyrA* serine 91 genotype real-time polymerase chain reaction with fluorescent hybridization probe detection assay, to meet the CLIA requirements, including accuracy, precision, limit of detection, interfering substances, and normal values. Full details of the verification protocol and *gyrA* serine 91 genotype assay standard operating procedure (SOP) are in the study's Manual of Procedures.

Specimens positive for gonococcal DNA or RNA from the participating clinical sites will be tested by PCR for detection of wild-type *gyrA* serine 91 genotype. Subjects who have been treated empirically (i.e., symptomatic subjects) may opt out of this testing, if indicated by the clinical site on the laboratory requisition.

The presence or absence of mutations in the *gyrA* gene will be determined by real-time PCR. For real-time PCR analysis of the *gyrA* gene, remnant NAAT specimens will be extracted, using either a Roche MagNAPure instrument or Qiacube, which will then be used for the *gyrA* real-time PCR, using a Roche LightCycler platform. The *gyrA* assay combines amplification of the *gyrA* gene in the serine 91 coding region and melting-curve analysis of to determine wild-type vs. mutation in this region. This is done through use of Fluorescence Resonance Energy Transfer (FRET) probes for the serine 91 amplicon.

8.2.2 Special Assays or Procedures for Enrolled Subjects

Urine collected at Visit 1 will be analyzed for detecting pregnancies by use of a standard rapid urine β hCG assay.

Swabs (non-cotton) will be used to collect specimens at each site (throat, rectal, urethral or cervical) for *N. gonorrhoeae* culture. The swab will be immediately smeared onto a modified Thayer Martin plate, which is placed into a candle jar or other CO₂-rich transport media, at the clinic. These plates will be transported in the CO₂-rich transport media to the local laboratory for culture for *N. gonorrhoeae*. The local laboratory will culture and isolate the gonococcal strain, according to their SOP for *N. gonorrhoeae* culture. *N. gonorrhoeae* culture specimens will be obtained first; this sequence maximizes the load collected, which increases the likelihood of a successful culture. A second swab or urine will be collected for NAAT for *N. gonorrhoeae* detection, according to the

laboratory SOP, using a collection kit with liquid transport specific to the local protocols (e.g. unisex swab specimen collection kit).

For each positive culture (regardless of anatomical site or visit number), a subculture of each gonococcal isolate will be subject to antimicrobial susceptibility testing using the agar dilution method for azithromycin, cefixime, ceftriaxone, ciprofloxacin, gentamicin, penicillin, spectinomycin, and tetracycline. M100 Clinical and Laboratory Standards Institute (CLSI) interpretive criteria will be used to evaluate susceptibility to each agent, with the exception of azithromycin, where CDC criteria will be used [16].

For each positive NAAT, or negative NAAT with a positive culture for the same visit, up to two 500 µL aliquots of the specimen will be frozen in screw-top 2.0 mL tubes, at -70°C for discordant resolution, if needed. These frozen remnants will be stocked at the local laboratory until they are sent to the central laboratories approximately halfway through the study and at study completion.

For subjects who demonstrate culture-based antibiotic resistance to ciprofloxacin but are deemed ciprofloxacin-susceptible by the *gyrA* gene-dependent mechanism, or have culture positivity at Visit 2, whole genome sequencing will be performed on their *N. gonorrhoeae* isolates from all visits. DNA samples will be extracted from the cultures and multiplexed libraries will be created. Sequencing will be performed according to the laboratory SOP using a platform such as the MiSeq (Illumina, San Diego, CA). Genomic assembly and annotation will be performed using sequenced *N. gonorrhoeae* strains as reference scaffolding and phylogenetic analyses will be conducted based on nucleotide polymorphisms [17].

Specific instructions and numbering schemes for study isolates and specimens are described in the study's Manual of Procedures.

8.2.3 Specimen Preparation, Handling, and Shipping

8.2.3.1 Instructions for Specimen Preparation, Handling, and Storage

Stocked clinical isolates of *N. gonorrhoeae* and remnant specimens will be stored at the performing laboratory site until they are sent to the central laboratories approximately halfway through the study and at the end of the study.

Specific instructions for specimen preparation, handling, and storage are described in the study's Manual of Procedures.

8.2.3.2 Specimen Shipment

Bacterial isolates will be shipped frozen on dry ice in accordance with IATA shipping regulations. *N. gonorrhoeae* DNA remnant specimens will be shipped to the reference laboratory frozen on dry ice at specified intervals in accordance with IATA shipping regulations. Specimens will be shipped as category B (infectious) substances to meet the requirements outlined in 49 CFR 178.609.

Specimens and isolates for use/long-term storage will be shipped to:

ATTN: [name], Laboratory Manager
University of California San Diego AVRC
XXXXXXXXXX

Specific instructions for specimen shipment will be described in the study's Manual of Procedures.

9 ASSESSMENT OF SAFETY

Ciprofloxacin has a well-established safety profile and has been prescribed to several millions of people in the US and worldwide as it was the CDC's recommended treatment regimen for uncomplicated gonorrhea from 1993 to 2007. Therefore, adverse event assessment is not required for this study.

In order to address the FDA Drug Safety Communication dated May 12, 2016, regarding fluoroquinolone use for certain uncomplicated infections, subjects will be asked at Visit 1, Visit 2, and any Unscheduled or Early Termination Visit if they have experienced any serious side effects related to fluoroquinolone use. These include tendon pain, joint pain, muscle pain, tingling or pricking sensation, confusion, and hallucinations. This information will be recorded in the study source documents as a change in health status. Any subject who experiences such an event will be given instructions on how to submit a MedWatch Consumer Voluntary Reporting Form to the FDA if they desire.

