3.3.5. Within Window Test of Cure Visit

Version 6.0 of the protocol (03 July 2018) was updated to expand the visit window for Visit 2 from Day 5-9 to Day 5-10. For subjects enrolled under version 6.0 (or later) of the protocol, the Test of Cure visit will be considered within window if the visit occurred between Days 5 and 10 (inclusive). For subjects enrolled under a version prior to version 6.0, Test of Cure visit will be considered within window if the visit occurred between Days 5 and 9 (inclusive).

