4.5.1. Safety Variables

Ciprofloxacin has a well-established safety profile and has been prescribed to several millions of people in the United States (US) and worldwide as it was the CDC's recommended treatment regimen for uncomplicated gonorrhea from 1993 to 2007. Therefore, adverse event assessment is not required for this study.

In order to address the FDA Drug Safety Communication dated May 12, 2016, regarding fluoroquinolone use for certain uncomplicated infections, subjects are asked at Visit 1, Visit 2, and any Unscheduled or Early Termination Visit if they have experienced any serious side effects related to fluoroquinolone use. These include tendon pain, joint pain, muscle pain, tingling or pricking sensation, confusion, and hallucinations. This information is recorded in the study source documents as a change in health status.

Any subject who experiences such an event is given instructions on how to submit a MedWatch Consumer Voluntary Reporting Form to the FDA if they desire.

Side effects of fluoroquinolone use will be summarized for all enrolled subjects (see Section 9).

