6. GENERAL STATISTICAL CONSIDERATIONS

6.1. General Principles

Tabulations will be used extensively to summarize the data. All continuous variables will be summarized using some or all of the following descriptive statistics: n (samples size), mean, standard deviation, median, maximum, and minimum. The frequency and percentages (based on the sample size) of observed levels will be reported for all categorical measures. Modified Jeffreys confidence intervals (CIs) for binomial proportions will be computed for efficacy variables [2]. A 5% one-sided significance level will be used; i.e. one-sided 95% confidence intervals will be generated. In general, all data will be listed, sorted by site and subject, and when appropriate by visit number within subject. All summary tables will be annotated with the total population size relevant to that table, including any missing observations.

Note that in the data listing, Subject ID is the unique subject identifier, not the Study ID used on study, and dates will not be included, only Study Day. Study Day 1 will be the day of the dose of treatment.

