The denominator of the percentage is the number of subjects whose assessments were collected at the particular visit.

The same subject may be counted at all visits.

*Only some subjects have data at Visit 3 due to the protocol amendment.

Table 35: Number and Percentage of Subjects with Prior and Concomitant Medications Contraindicated with Ciprofloxacin or Systemic Antibiotics by WHO Drug Classification—All Enrolled Subjects

WHO Drug Code Level 1, Anatomic Group	WHO Drug Code Level 2, Therapeutic Subgroup	All Subjects (N=X)	
		n	%
Any Level 1 Codes	Any Level 2 Codes	x	x
[ATC Level 1 - 1]	Any	x	x
	[ATC 2 - 1]	x	x
	[ATC 2 - 2]	x	x
	[ATC 2 - 3]	x	x
[ATC Level 1 – 2]	Any	x	x
	[ATC 2 - 1]	x	x
	[ATC 2 - 2]	x	x
	[ATC 2 - 3]	x	x

N= Number of all enrolled subjects

n=Number of subjects reporting taking at least one medication in the specific WHO Drug Class.

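### The six fluoroquinolone symptoms are asked about at only one scheduled post-dose contact (Visit 2); adding them to the existing Day 11-14 call would be a cheap improvement

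*Protocol*

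**What the plan says.** Protocol section 9 dispenses with general adverse event collection because ciprofloxacin is long used and well characterised. In response to a 2016 FDA safety communication it keeps one targeted enquiry, covering six symptoms: tendon, joint and muscle pain, tingling or pricking, confusion, and hallucinations. On timing, "subjects will be asked at Visit 1, Visit 2, and any Unscheduled or Early Termination Visit if they have experienced any serious side effects". SAP 4.5.1 repeats the schedule ("subjects are asked at Visit 1, Visit 2, and any Unscheduled or Early Termination Visit") and adds that "Side effects of fluoroquinolone use will be summarized for all enrolled subjects".

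Visit 3 (protocol 7.3, Day 11-14) is a telephone contact: "Test results will be provided to subjects by phone call". Its other items are closing out negative subjects, referring positive ones and a reminder about partners. In protocol Appendix A and SAP Table 2, the symptom-history row is marked at Visit 1, Visit 2 and Unscheduled/Early Termination, and is blank at Visit 3.

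SAP Table 34, which reports the six symptoms, has columns for Visits 1, 2 and 3. The Visit 3 column is footnoted: "Only some subjects have data at Visit 3 due to the protocol amendment". The Listing 14 shell shows only Visits 1 and 2, but carries the same note about Visit 3.

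**The concern.** The sponsor chose these six symptoms as the ones worth asking about, and the protocol already has subjects telephoned at Day 11-14. Yet the questions stop at Visit 2, which can fall as early as Day 5. A symptom that begins between Visit 2 and the call is not solicited at any scheduled contact. It enters the data only if the subject has an unscheduled or early termination visit.

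What is at stake is the completeness of a small descriptive safety summary. The length of solicited follow-up also varies between subjects, with the day on which Visit 2 fell and with the protocol version in force at the time.

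**Working it through.** The plan states no figure for length of safety follow-up, so there is none to reproduce. The check is day arithmetic and a comparison of sections.

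**Which contacts come after the dose.** In protocol 7.1 the symptom history is item 3 and the dose is item 15. Protocol 8.1 also places the Visit 1 history before treatment. Visit 1 answers are therefore baseline, and Visit 2 is the only scheduled post-dose enquiry.

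**Elapsed time.** SAP 6.1 fixes the numbering: "Study Day 1 will be the day of the dose of treatment". Hence days since dose = Study Day - 1.

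- Visit 2, earliest: 5 - 1 = 4 days.
- Visit 2, latest: 10 - 1 = 9 days.
- Visit 3 call, earliest: 11 - 1 = 10 days.
- Visit 3 call, latest: 14 - 1 = 13 days.

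SAP 3.3.5 records that protocol version 6.0 was changed to "expand the visit window for Visit 2 from Day 5-9 to Day 5-10". Before that change the latest in-window Visit 2 was 9 - 1 = 8 days after the dose. The earliest stays at 4.

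**Gain from asking at the call.** Added days = Visit 3 day - Visit 2 day.

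- Minimum: 11 - 10 = 1 day.
- Maximum: 14 - 5 = 9 days.

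**Day convention.** Protocol 11.1 describes cure at 5 to 10 days after receiving the drug. Read literally, that makes the earliest Visit 2 five days after the dose, not four. The two descriptions should be reconciled. If one convention is applied to both visits, the gain of 1-9 days does not change.

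**Reporting.** The current protocol collects no symptoms at Visit 3, yet Table 34 has a Visit 3 column filled for some subjects. The natural inference is that those data were collected under an earlier version. The documents identify neither the amendment nor the size of the subset. Table 34 does not separate versions and has no column for unscheduled or early termination reports. The Listing 14 shell has no Visit 3 row, although its note refers to Visit 3 data.

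**The case against.** The strongest reply is that this is a stated choice. Section 9 gives its reason, the drug is described as approved for gonorrhea, no objective or outcome measure concerns safety, and SAP 6.3.1 says there is no formal safety analysis. Protocol section 9, 7.3, Appendix A and SAP 4.5.1 agree with one another. All of this stands, and it is why the point is an improvement and not an error. The stated reason explains dropping general adverse event collection. It does not explain leaving six questions already judged worth asking off a call that is made anyway.

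A reader might infer that the six questions are the trial's only harm data. The documents do not support that. Visit 2 also includes an interim history that is to cover new medical conditions (protocol 8.1) and a targeted examination. SAP 9.5 lists musculoskeletal and neurological systems among those examined, with abnormal findings in Listing 16. Unscheduled visits remain a route for later symptoms.

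A reader might also infer that Table 34 passes for complete three-visit follow-up. It does not: the footnote discloses the partial Visit 3 data, and each column's denominator is already the number of subjects assessed at that visit. What remains is that the Visit 3 results are not shown by protocol version and Listing 14 does not match.

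Finally, a late change creates one more group of subjects with a different collection history. That is true, and it is a reason to report by version.

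**Conclusion.** The point holds as an optional, low-cost improvement. After the dose, the six symptoms are solicited at one scheduled contact, 4-9 days out, while a call already planned at 10-13 days is not used for them. Asking then would add 1-9 days of solicited follow-up per subject reached. These figures assume visits within window and the SAP's day numbering. No efficacy estimate, power or sample size changes.

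It is tempting to convert the gap into a number of missed events. The documents do not allow it. They give no risk for these symptoms after a single dose, no onset pattern, and no rate of Visit 2 attendance or of telephone contact. The 10% allowance in the sample-size section covers exclusion from the per-protocol population for several reasons, so it cannot stand in for non-attendance. The gain is also small for a subject seen on Day 10 and called on Day 11. The size should be stated in days, not events.

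**What to change.** 1. For subjects not yet past Visit 3, add the six symptom questions, worded to cover the time since the last visit, to the Visit 3 call. This touches protocol 7.3, section 9 and Appendix A, and SAP 4.5.1 and Table 2.
2. In SAP Table 34, show Visit 3 results by protocol version, and keep the existing denominator of subjects assessed at that visit.
3. Align the Listing 14 shell with its own note by allowing Visit 3 rows.

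The cost is a minor amendment and a few minutes on a call already planned, with no new visit or specimen. Some subjects will not be reached by phone, so the Visit 3 denominator will be smaller than that for Visit 2. Subjects already past Visit 3 cannot be recovered, and for them only the reporting changes apply. If enrolment is too far advanced for an amendment to be worthwhile, items 2 and 3 can be done in the SAP alone.

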10 CLINICAL MONITORING

10.1 Site Monitoring Plan

Site monitoring is conducted to ensure that the human subject protections, study and laboratory procedures, study intervention administration, and data collection processes are of high quality and meet sponsor requirements, ICH/GCP guidelines and applicable regulations, and that the study is conducted in accordance with the protocol, protocol-specific Manual of Procedures and applicable sponsor standard operating procedures. DMID, the sponsoring agency, or its designee, will conduct site-monitoring visits as detailed in the clinical monitoring plan.

Site visits will be made at standard intervals as defined by DMID and may be made more frequently as directed by DMID. Monitoring visits will include, but are not limited to, review of regulatory files, accountability records, electronic case report forms (eCRFs), informed consent forms, source documents necessary to support the documentation entered into the eCRFs, and protocol and GCP compliance. Site monitors will have access to the study site, study personnel, and all study documentation according to the DMID-approved site monitoring plan. Study monitors will meet with site principal investigators to discuss any problems and actions to be taken and will document visit findings and discussions.

